CHW Recruitment: We will hire and train 6 CHWs (3@VA, 3@BH), from local patient support organizations (Veteran Service Organizations and BH volunteer office, as we have done in prior CHW studies) to implement the toolkit strategies. CHW employment opportunities announcements will be created. Requirements will include: 1) evidence of a leadership role in the patient community through social support or advocacy organizations; 2) strong communication and interpersonal skills; and 3) a high school education or GED. CHW candidates will not be required to have a background in health. Personal experience with DM will not be required.

CHW Training: We will train the CHWs in key DM concepts, motivational interviewing, brief action planning, and stages of behavior change. CHWs will participate in a 105-hour core competency training developed collaboratively developed by [name] and her team and the Community Health Worker Network of New York. CHWs will conduct mock telephone counseling calls with trained standardized patients to enhance skills, gain feedback, and develop confidence in these techniques. In addition to these training experiences, CHWs will have letter templates, motivational interviewing scripts, and protocols available for patient outreach to standardize and guide patient outreach

CHW Intervention

At each wave's outset, ~ 250 patients at each study site will be randomly selected for outreach and paired with one of five CHWs (2 at BH, 2 at VA, 1 at both clinics). Researchers will provide each intervention group PC provider their selected list of prediabetic patients. PCPs will be asked to review the list to identify anyone they think should be excluded from the intervention. Patients are matched to a CHW according to the patient's language and neighborhood of residence, as the study aims to cluster CHWs' patients to facilitate CHW travel and expertise in local resources. We mail selected patients a letter on behalf of their PCP alerting them of their DM risk status, available prevention resources, and introducing them to their assigned CHW. CHWs will then call patients to describe the program and seek verbal informed consent to enroll in the study. Patients who decline participation will be asked if they are willing to be invited again in subsequent waves of the study. CHWs will continue outreach until they have met their caseload for the wave.

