We developed a toolkit of strategies for pre-DM coaching outreach to standardize the intervention across CHWs and to focus on evidence-based strategies for preventing DM. The toolkit was adapted from the version we developed and used in the PROVE study aiming to improve outcomes in HTN and smoking. The toolkit interventions reflect standards of care and can be selected and tailored for the broad population of pre-DM patients. We will enhance uptake and effectiveness of services by employing CHWs to regularly contact, counsel, remind, and follow-up with patients. Outreach strategies will be tailored to patients' health care needs and their stage of activation. CHWs will deliver outreach based on patient preferences and activation level, as there is evidence that the fit between an intervention and a patient's motivations, beliefs and perceptions encourages activation, goal setting and ultimately behavior change. During their first contact with patients, CHWs will use a standardized, 6-item questionnaire (PAM-6) to quickly assess patients' activation level. Thus, CHWs will offer toolkit strategies that best fit the patients' level of activation, matching patients with the most intensive intervention they are ready to accept. Standardized protocols will also be used to ensure that CHWs dedicate sufficient time to engaging patients with lower levels of activation.

Within the 3-year intervention period, each patient's 12-month CHW intervention will consist of a 6-month intensive phase followed by a 6-month maintenance phase, as described below.

- *Phone Call:* CHWs will call eligible pre-DM patients and ask to obtain informed consent (in accordance with our waiver of documentation of consent) to participate in the study, fully describing the study and reviewing all elements of consent. If the patient consents, CHWs will conduct the intake process, which includes a survey, the PAM, and a conversation about health goals. CHWs encourage the patient to engage in the most intensive strategy that is matched to their activation level and health goals (Health Action Plan).

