Process indicators: In this pragmatic trial, we will systematically track and examine the process of implementation and the contextual factors that influence implementation of the CHW intervention. To do so, we will draw on available study data in REDCap, the secure program used to record CHW-patient encounters for the study. At the end of the study we expect to have data on approximately 1,000 enrolled intervention patients, with each patient followed for one year, with CHW-patient contacts limited to the intensity that patients are willing to attend. From REDCap, we will collect data semi-annually on four indicators of implementation fidelity, namely (1) the content of CHW activities, (2) the coverage (number of patients reached), (3) duration (how long each patient is followed up), and (4) frequency (how often patients are contacted) of CHW-patient contacts. Content of CHW activities will be assessed through assessing CHW case notes on a random selection of 15 enrolled patients and interviews with CHWs. Case notes will be assessed to examine how CHWs handle patients' behavioral barriers and social needs, including the referrals they make to various services (e.g., mental health, social work, exercise programs). To understand barriers that CHWs confront in the course of implementation, we will conduct semi-structured interviews with the CHWs and identify major themes (questions, concerns) related to behavioral counseling and referrals that may be discussed during the study team's meetings and case conferences. Similar to the semi-structured interviews with providers and other primary care team members, interviews will be conducted at end of year 1, 1.5, 2, 2.5, and 3. Findings resulting from analysis of patient case notes and other CHW materials will be reported anonymously.

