Staff survey data will be used to assess the self-efficacy and collective-efficacy as a team in preventing DM and in working with a CHW coach. We will compare baseline and post-intervention scores on each of the measures. To test the hypothesis that staff assigned to the intervention teams who work closely with a CHW will improve their self and collective efficacy of DM prevention and CHW coaching, we will compare post-intervention scores for these measures across the study arms using linear regression and controlling for baseline scores and adjusting for staff roles, length of time in their role and site. Survey data will also be used to assess PCPs' readiness to work with CHWs for DM prevention. Baseline and post-intervention scores will be compared using Wilcoxon signed-rank tests.

All interviews transcripts (from PCMH and other staff, practice administrators, CHWs, and key informants) and observations of study team meetings and case conferences will be analyzed for common themes by two independent researchers for qualitative analysis. First, two researchers will read the transcripts to identify key domains. Second, the researchers will independently code two of each set of transcripts. They will then meet to develop initial codebooks with code names and meanings. Third, each coder will apply the codebook to the remaining transcripts. Fourth, coders will meet to compare codes and identify patterns and common themes throughout the transcripts. Baseline interviews will be used to guide toolkit refinement and to explore anticipated facilitators and barriers to incorporating CHWs into the PCMH workflow. Mid- and post-intervention interview data will help us to determine key barriers, facilitators and lessons learned from staff, CHWs, and key informants regarding the implementation of CHWs in PC practice.

To assess implementation fidelity, baseline and 6-monthly scores on the coverage, duration, and frequency of CHW-patient contact for BH and VA patients will be compared using ANCOVA. Content of delivery will also be assessed qualitatively based on a sample of CHW-patient contacts. Implementation fidelity will be compared across BH and the VA to examine if differences in organizational setting shape the implementation process.

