Data from the FACETS neighborhood database of social determinants will be conjoined with study data to describe whether contextual factors pertaining to NYC neighborhoods are associated with prediabetes prevalence across neighborhoods. We will use a multilevel statistical model, with patients nested within neighborhoods, to conduct this analysis.

Process Evaluation: To ensure that the intervention was delivered completely and standardized across the sites, CHWs and clinical teams, there will be continuous monitoring of process outcomes and fidelity to the protocol during the CHW intervention. We will maintain standardized protocols for each toolkit strategy and documentation of peer coaching. The CHW Coordinator will conduct quarterly assessments of the interventions, proportion of patients reached and engaged by site and CHW, fidelity to counseling protocols, and the preferred toolkit and contact strategies.

Statistical Power and Sample Size

The primary study outcome for power calculations is the annual hazard rate of incident DM.

To determine sample size, we begin with the total accessible population of about 46,000 primary care patients served at the two sites (BH and VA). Of these we exclude patients with diagnosed DM (25% at VA and 15% at BH) and those over 75 years of age (who are ineligible for this intervention). Of these eligible subjects, we estimated that about 70% will have had the HbA1c test in the last 2 years and that about 40% of these will have had a test result in the prediabetes range.

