While the above inclusion and exclusion criteria return about 9,300 eligible patients, 8,200 at BH and 1,100 at the VA, CHW caseload limitations preclude us from reaching all these eligible patients during the 3-year intervention. Assuming a caseload of 72 patients per fulltime CHW per wave (with 3.5 fulltime equivalent CHWs across both sites and 4 waves), the intervention is projected to enroll a minimum of 1,008 subjects into the intervention group. An equivalent number of subjects will be randomly selected from the Control teams for a total of at least 2,016 study subjects overall. The intervention and control subjects will be split across the two study sites. After assuming that we will not be able to reach about 20% (due to missing or incorrect contact information) unreachable rate, and that about 60% will consent to enroll in the intervention, we will randomly select about double the 1,008 subjects (about 2,100) for potential enrollment into the intervention in order to enroll the minimum of 1,008 intervention subjects needed to have adequate statistical power.

Power: In the pre-DM population we estimate the 3-year DM incidence to be 15% (based on preliminary analysis of a similar VA cohort from 2010-2012). Based on our analyses, with 1,008 patients allocated to each of the intervention and control groups, we anticipate having 80% power ($\alpha = 0.05$) to detect a difference in time-to-event (DM incidence) between the intervention and control group.

To assess measures of implementation fidelity, specifically coverage, duration, and frequency of CHW-patient contact, we will base calculations on all patients enrolled. Since we will use all available study data from the electronic medical records, power and sample size considerations do not apply. We will assess content of CHW-patient contact using qualitative methods, hence power and sample size considerations do not apply.

To examine the variation in prediabetes prevalence across NYC neighborhoods, we will use available data from BH at the start of the study, in approximately 19,000 patients. These patients meet the study's previously stated eligibility criteria, with two modifications: patients must have (1) any HbA1c result in the past 5 years and (2) an address available in the EHR. Data on all enrolled BH patients at the end of the study, an estimated 1,000 patients, will also be used. Since we will use all available study data, power and sample size considerations do not apply.

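### Fidelity coverage is calculated on enrolled patients only, so the planned Bellevue–VA comparison cannot show a difference in outreach reach or consent yield

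*Combined protocol and SAP*

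**What the plan says.** **Coverage**

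- Process indicators (under Implementation Research) lists four fidelity indicators. The second reads "2) the coverage (number of patients reached". The same paragraph expects REDCap data on roughly 1,000 enrolled intervention patients.
- Statistical Power and Sample Size sets the base for three of the four: "specifically coverage, duration, and frequency of CHW-patient contact, we will base calculations on all patients enrolled".
- Analysis: Intervention Implementation states the comparison: "baseline and 6-monthly scores on the coverage, duration, and frequency of CHW-patient contact for BH and VA patients will be compared using ANCOVA". Its purpose is to see whether organisational setting shapes implementation.
- The Process Evaluation paragraph has the CHW Coordinator assess each quarter the "proportion of patients reached and engaged by site and CHW". It gives no denominator.

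**Enrolment**

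- CHW Intervention: "CHWs will then call patients to describe the program and seek verbal informed consent to enroll in the study". The Phone Call bullet adds: "If the patient consents, CHWs will conduct the intake process".
- For refusals: "Patients who decline participation will be asked if they are willing to be invited again in subsequent waves of the study". For the stopping rule: "CHWs will continue outreach until they have met their caseload for the wave".
- Number of Subjects assumes that 20% cannot be reached and that 60% of those reached will enrol.

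**Consent and re-call**

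- Method of Subject Identification and Recruitment, and Consent says that patients give no individual consent to calls, letters or other CHW contact. It then treats a patient's continued dealings with the CHW as informed consent.
- A later CHW Intervention bullet has patients who are not ready to change behaviour at the first call rung again at six-month intervals unless they opt out. It does not say whether they have consented.

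**The concern.** Coverage should tell the reader how far the programme got into the population it was aimed at. In the plan's own recruitment assumptions, being reached is a step that comes before enrolling. If coverage is then calculated only on people who have enrolled, the patients who could not be reached, and those who were reached and said no, drop out of the measure. Those are the patients in whom two sites would differ if one had worse contact data or a less receptive population.

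At stake is the implementation aim, not the clinical outcomes. Assessing how CHWs are recruited, trained and integrated is a stated study aim, and the BH–VA contrast is one of its planned analyses. One of its quantitative indicators would say nothing about outreach.

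The consent wording is a separate matter. A CHW, or an ethics board, should find one rule on whether coaching needs the patient's verbal agreement. The document gives two.

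**Working it through.** **Inputs**

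- Selected for outreach: about 2,100 (Statistical Power and Sample Size).
- Unreachable: 20% (same section, and Number of Subjects).
- Enrol: 60% of those reached (Number of Subjects gives this base).
- Caseload: 72 patients per full-time CHW per wave, 3.5 full-time equivalents, 4 waves (Statistical Power and Sample Size).
- Assumption: all 2,100 selected are attempted.

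**Step 1. Reproduce the plan's figure of 1,008.**

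- By caseload: 72 × 3.5 × 4 = 1,008.
- By outreach: 2,100 × (1 − 0.20) × 0.60 = 1,008.

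Both routes agree with the stated minimum. Applying 60% to everyone selected would give 2,100 × 0.60 = 1,260, which does not agree. So the 60% is of those reached, and reaching precedes enrolling.

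**Step 2. Lay out the outreach funnel.**

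- Reached: 2,100 × 0.80 = 1,680, or 80% of those selected.
- Not reached: 2,100 − 1,680 = 420.
- Enrolled: 1,008, or 1,008/2,100 = 48% of those selected.
- Reached but not enrolled: 1,680 − 1,008 = 672, or 672/1,680 = 40% of those reached.

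**Step 3. Compare the two bases for coverage.** Let r be the share reached and c the share of reached patients who consent.

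- On patients selected: reach = r and yield = r × c. Both respond to what happens during outreach.
- On patients enrolled: the share reached is 1,008/1,008 = 100%. Enrolling requires a consent call, so this is 100% at first contact whatever r and c are.

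As an illustration with an assumed rate, if r stays at 0.80 and c falls from 0.60 to 0.40, yield falls from 48% to 0.80 × 0.40 = 32%. Coverage on the enrolled base stays at 100%.

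**Step 4. Later scores.** A six-monthly score of enrolled patients contacted in the period can fall below 100% and can differ by site. It describes continued contact among consenters. It contains no information on r or c.

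**Step 5. Other figures in the plan.** CHW Intervention gives about 250 per site per wave. That is 250 × 2 × 4 = 2,000 selected, 1,600 reached and 960 enrolled, with 640 reached but not enrolled. Number of Subjects gives about 1,100 enrolled. The number reached but not enrolled is then 1,680 − 1,100 = 580, or 1,100/0.60 − 1,100 ≈ 733 if the 60% is kept. The counts move, but the argument in step 3 does not.

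**Step 6. Consent text side by side.** CHW Intervention makes enrolment and intake conditional on verbal agreement during the call. The consent section needs no individual agreement for any CHW contact and infers consent from continued interaction. Letters and a first call without prior consent fit both. Coaching calls do not: they are CHW contact, and they follow intake.

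**The case against.** The best reply on coverage is that the text can be read consistently. Process indicators speaks of data on about 1,000 enrolled patients and of semi-annual collection. Coverage may there mean enrolled patients contacted in each period, which matches the enrolled base and the six-monthly scores. This reading is available, and it means that 1,680 against 1,008 is not a proven conflict between two stated values of coverage. It does not rescue the measure, because it is the reading under which outreach is invisible.

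A second reply is that the quarterly monitoring already captures reach by site. That shows the data can be had. It has no stated denominator, and it is not the comparison specified in the analysis section.

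A third is that the count enrolled can differ by site, since 1,008 is a projected minimum. True, but CHWs keep going until caseload is filled. A shortfall would show that a caseload was not met, not whether reach or consent was the cause.

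Three stronger readings are tempting, and the documents do not support them.

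- A reader might infer that all 672 patients reached without consenting have no settled status. Those who refuse outright are plainly not enrolled, and CHW Intervention says how they may be re-invited. Only patients who neither agree nor refuse, or who are not ready and whose consent is unstated, are unclear. The plan gives no number for them: at most 672 on the sample-size figures, and possibly near zero.
- A reader might see the two re-contact rules as contradictory. They are worded for different groups: those who decline, and those not ready to change. The gap is that the second group's consent status is not stated, which is an ambiguity.
- A reader might carry the consent conflict into the trial's main analysis. Nothing in the text enrols a patient through continued contact, so the planned arm remains about 1,008.

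**Conclusion.** The concern stands in limited form. With coverage calculated on enrolled patients, the score is 100% at first contact by construction, and later scores vary only among consenters. The planned BH–VA comparison therefore cannot reveal a difference in reach (80% on the plan's assumptions) or in yield (48%). This rests on enrolment occurring only through a consent call, as CHW Intervention states. It does not depend on the exact outreach numbers.

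The conflict over consent is a genuine contradiction in the text and needs one rule. The status of patients who are not ready is a smaller ambiguity. The consequences are confined to the fidelity assessment and to consent practice; no effect on the intention-to-treat set, arm size or power follows.

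**What to change.** 1. In Statistical Power and Sample Size, base coverage on all patients selected and attempted. Report the numbers attempted, reached and consented by site and wave, and compare BH with VA on reached/attempted and consented/attempted. Keep duration and frequency on enrolled patients. Align Process indicators, the analysis section and the quarterly monitoring with the same denominator.
2. Reword the consent section to match CHW Intervention: letters and the first call need no prior consent; enrolment and coaching need verbal consent on the call. Opting out remains possible at any time.
3. In the re-call bullet, state whether the patients who are not ready have consented. If some have not, record them as undecided and not enrolled, and give the re-contact rule for them.

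The cost is one status code per patient attempted (not reached, declined, undecided, consented) and a short amendment. No extra patients or visits are needed, since the outreach lists exist and reach is already monitored. The code should be entered at the time of the call, because it would be hard to reconstruct later.
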